### **5.2.2. Analyses for Continuous Data**

#### Descriptive Summary:

The following statistics will be presented: number of subjects, mean, standard deviation, median, minimum, and maximum. The 2-sided 95% CI will be also produced, if necessary.

#### Estimations:

##### **Geometric Mean (GM)**

For each serotype, OPA GMTs and IgG GMCs will be calculated. The serotype-specific OPA titers and IgG concentrations will be logarithmically transformed for analysis. GMTs or GMCs will be back transformations of the mean of the log-transformed measures. Two-sided 95% CIs will be constructed by back transformation of the CIs for the mean of the logarithmically transformed assay results computed using the Student t distribution.

##### **Geometric Mean Fold Rise (GMFR)**

For each serotype, OPA and IgG GMFRs will be calculated. The serotype-specific OPA titers or IgG concentrations will be logarithmically transformed for analysis. GMFRs will be back transformations of the mean of the difference of the log-transformed measures (1 month after vaccination – prevaccination). Two-sided CIs for GMFRs will be back transformations of a CI based on the Student t distribution for the mean difference of the log-transformed measures.

##### **Reverse Cumulative Distribution Curve (RCDC)**

For each serotype, the empirical reverse cumulative distribution curves (RCDCs) will plot the percentage of subjects achieving a given titer or concentration.

### 5.3. Methods to Manage Missing Data

For the analysis of the immunogenicity endpoints, missing values will be retained as missing and will not be imputed.

Handling of missing values for local reactions and systemic events is described in [Section 6.1.1.1](#) and [Section 6.1.1.2](#).

### 5.4. Methods to Manage Data Below the Lower Limit of Quantitation (LLOQ)

#### OPA Titer

Pfizer's OPA lower limit of quantitation (LLOQ) was defined from the GMT of the lowest titer values established during the validation that demonstrated acceptable linearity (relative accuracy) and precision as defined in the validation protocol MVP-1020. The LLOQ titer for each serotype was set as in Table 2.

OPA titers above the LLOQ are considered accurate and their quantitated values will be reported. Titers below the LLOQ or denoted as below the limit of quantitation (BLQ) will be set to  $0.5 \times \text{LLOQ}$  for analysis.

#### IgG Concentration

Pfizer's Luminex IgG LLOQs in micrograms per mL ( $\mu\text{g/mL}$ ) for each serotype are set as in Table 2. Antibody concentrations above the LLOQ are considered accurate and their quantitated values will be reported. Values below the LLOQ or denoted as BLQ will be set to  $0.5 \times \text{LLOQ}$  for analysis.

**Table 2. Lower Limit of Quantitation of Antibody Level for Each Serotype**

Antigen	OPA LLOQ	IgG LLOQ
1	18	0.002
3	12	0.004
4	21	0.005
5	29	0.002
6A	37	0.005
6B	43	0.015
7F	113	0.003
9V	141	0.013
14	35	0.005
18C	31	0.002
19A	18	0.038
19F	48	0.012
23F	13	0.009

Abbreviations: IgG = immunoglobulin G; LLOQ = lower limit of quantitation; OPA = opsonophagocytic activity.

090177e190dcce77Approved\Approved On: 06-May-2019 11:24 (GMT)

## 6. ANALYSES AND SUMMARIES

### 6.1. Primary Endpoints

#### 6.1.1. Safety Summaries and Analyses

- Number and proportion of subjects reporting local reactions (redness, swelling, pain at injection site) and severity of the local reactions occurring within the 7-day period following study vaccination in the 6- to <18-year age group.
- Number and proportion of subjects reporting local reactions (redness, swelling, pain at injection site) and severity of the local reactions occurring within the 14-day period following study vaccination in the 18- to <65-year age group.
- Number and proportion of subjects reporting systemic events (fever, fatigue, headache, vomiting, diarrhea, muscle pain, joint pain) and severity of the systemic events occurring within the 7-day period following study vaccination in the 6- to <18-year age group.
- Number and proportion of subjects reporting systemic events (fever, fatigue, headache, vomiting, diarrhea, muscle pain, joint pain) and severity of the systemic events occurring within the 14-day period following study vaccination in the 18- to <65-year age group.
- Number and proportion of subjects reporting AEs and SAEs until Visit 2 categorized according to MedDRA in all age groups.

##### 6.1.1.1. Local Reactions

**Endpoints:** Number and proportion of subjects reporting local reactions (redness, swelling, pain at injection site) and severity of the local reactions.

- Analysis time points: The 7-day period (6- to <18-year age group) and 14-day period (18- to <65-year age group) following study vaccination.
- Analysis population: Safety population (Definitions of denominators for the summary tables are described in each reporting summary section).
- Subgroups: Each age group (6 to <18 years old and 18 to <65 years old) and each age category (6 to <12 years old, 12 to <18 years old, 18 to <50 years old, and 50 to <65 years old) in each age group.

For each local reaction, severity will be derived by the maximum severity grade of the reaction based on the severity grading scale of the local reactions in Table 3 for subjects aged 6 to <12 years, and Table 4 for subjects aged 12 to <18 years and those aged 18 to <65 years.

**Table 3. Local Reaction Grading Scale (Subjects Aged 6 to <12 Years)**

	GRADE 1 mild	GRADE 2 moderate	GRADE 3a severe	GRADE 4b
Redness	1 to 4 caliper units (or measuring device units) 0.5 to 2.0 cm	>4 to 14 caliper units (or measuring device units) >2.0 to 7.0 cm	>14 caliper units (or measuring device units) >7.0 cm	Necrosis or exfoliative dermatitis b
Swelling	1 to 4 caliper units (or measuring device units) 0.5 to 2.0 cm	>4 to 14 caliper units (or measuring device units) >2.0 to 7.0 cm	>14 caliper units (or measuring device units) >7.0 cm	Necrosis b
Pain (tenderness) at the injection site	Does not interfere with activity	Interferes with activity	Prevents daily activity	Emergency room visit or hospitalization for severe pain (tenderness) at the injection site

Abbreviations: CRF = case report form; e-diary = electronic diary.

Note: If the size of the redness and/or swelling falls between 2 caliper units, the higher caliper unit number will be recorded in the e-diary.

- a. When subjects experience local reactions >14 caliper units (>7.0 cm) or severe pain (tenderness) at the injection site, the subject/legally acceptable representative/parent/legal guardian will telephone the study site. In the event that the subject/legally acceptable representative/parent/legal guardian does not call, the investigator will call the subject/legally acceptable representative/parent/legal guardian.
- b. Grade 4 assessment should be made by the investigator and recorded as an AE on the CRF.

090177e190dcce77Approved\Approved On: 06-May-2019 11:24 (GMT)

**Table 4. Local Reaction Grading Scale (Subjects Aged 12 to <18 Years and 18 to <65 Years)**

	GRADE 1 mild	GRADE 2 moderate	GRADE 3a severe	GRADE 4b
Redness	5 to 10 caliper units (or measuring device units) 2.5 to 5.0 cm	>10 to 20 caliper units (or measuring device units) >5.0 to 10.0 cm	>20 caliper units (or measuring device units) >10.0 cm	Necrosis or exfoliative dermatitis b
Swelling	5 to 10 caliper units (or measuring device units) 2.5 to 5.0 cm	>10 to 20 caliper units (or measuring device units) >5.0 to 10.0 cm	>20 caliper units (or measuring device units) >10.0 cm	Necrosis b
Pain at the injection site	Does not interfere with activity	Interferes with activity	Prevents daily activity	Emergency room visit or hospitalization for severe pain at the injection site

Abbreviations: CRF = case report form; e-diary = electronic diary.

Note: If the size of the redness and/or swelling falls between 2 caliper units, the higher caliper unit number will be recorded in the e-diary.

- a. When subjects experience local reactions >20 caliper units (>10.0 cm) or severe pain at the injection site, the subject/legally acceptable representative/parent/legal guardian will telephone the study site. In the event that the subject/legally acceptable representative/parent/legal guardian does not call, the investigator will call the subject/legally acceptable representative/parent/legal guardian.
- b. Grade 4 assessment for local reactions should be made by the investigator and recorded as an AE on the CRF.

**Reporting Summaries:**

➤ Summary of Subjects Reporting Local Reactions by Maximum Severity Grade of the Reaction

The number of subjects reporting “yes” for at least 1 day or “no” for all days (these values are used as the denominators for the percentage calculations), number of subjects reporting at least 1 occurrence of the specified reaction or any reaction by the maximum severity grade, observed proportion of subjects, and their exact 2-sided CIs (Clopper and Pearson).

The above is repeated for moderate or severe reactions.

**Analysis Specifications**

The severity (grading) scales for redness and swelling are different between subjects 6 to <12 years of age and 12 to <18 years of age. The age-appropriate grading scale will be used for each subject, and the combined data will be summarized as the 6- to <18-year age group.

090177e190dcce77ApprovedApproved On: 06-May-2019 11:24 (GMT)

For each local reaction on any day, Table 5 provides the algorithm to derive the presence of a reaction (yes or no) during Day 1 to Day 7 (6- to <18-year age group) or Day 14 (18- to <65-year age group) following vaccination, where Day 1 is the day of vaccination.

**Table 5. Derived Variables for Each Local Reaction Within the Time Interval**

Variable a	Yes (1)	No (0)	Missing (.)
Any day (Day 1 to Day 7 or 14)	Subject reports the specific reaction in the required interval.	Subject reports the specific reaction as none (or absent) for all days in the required interval.	Subject reports the specific reaction as a combination of none and missing for all days in the required interval.

- a. The variable will be derived for each of the local reactions and (redness, swelling, and pain at the injection site) and for each of the severe or greater local reactions within Day 1 to Day 7 or 14 following vaccination.

For any local reaction on any day, a similar rule applies as specified in Table 6:

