**Table 6. Derived Variables for Any Local Reaction Within the Time Interval**

Variable a	Yes (1)	No (0)	Missing (.)
Any day (Day 1 to Day 7 or 14)	Subject reports any reaction as yes (or present) on any day in the required interval.	Subject reports all reactions as none (or absent) for all days in the required interval.	Subject reports all reactions as a combination of none and missing for all days in the required interval.

- a. The variable will be derived for any local reaction (any of redness, swelling, and pain at the injection site) and for any severe or greater local reaction within Day 1 to Day 7 or 14 following vaccination.

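### Does the lack of a grade for 1 to 4 caliper units of redness or swelling from age 12 upset the primary local-reaction counts?

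*SAP*

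**What the plan says.** Protocol 6.1 and 7.2.1.3 give subjects aged 12 and over a caliper reading from 1 to 21+ units, at 0.5 cm per unit. Protocol 7.2.1.3 adds that the readings are afterwards sorted into mild, moderate or severe on the scale for the age.

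For ages 12 to <65, Grade 1 redness or swelling in SAP Table 4 is "5 to 10 caliper units (or measuring device units) 2.5 to 5.0 cm". For ages 6 to <12, Grade 1 in SAP Table 3 is "1 to 4 caliper units (or measuring device units) 0.5 to 2.0 cm".

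Presence is derived in SAP Tables 5 and 6. In Table 5, Yes is "Subject reports the specific reaction in the required interval" and No is "Subject reports the specific reaction as none (or absent) for all days in the required interval". For any local reaction, Table 6 has Yes when "Subject reports any reaction as yes (or present) on any day in the required interval". Neither table names a size or a grade as the threshold for presence.

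Severity is a separate step in SAP 6.1.1.1: "For each local reaction, severity will be derived by the maximum severity grade of the reaction based on the severity grading scale". The main summary then gives the "number of subjects reporting at least 1 occurrence of the specified reaction or any reaction by the maximum severity grade", with exact confidence intervals.

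**The concern.** An adult whose redness never exceeds 3 units has reported redness but has no place on the grading scale. A child of 10 with the same reading is Grade 1. No section says whether the adult belongs with the mild reactions, in a row of their own, or with the subjects who had no reaction.

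The proportions with redness and with swelling, and their severity, are primary endpoints (Protocol 2, SAP 2.1). If presence follows Tables 5 and 6 while severity follows Table 4, the grade rows can total less than the number with the reaction. If a programmer instead required a grade before coding Yes, the reported incidence would be lower than the tables intend. In a descriptive, single-arm study these proportions are the result, so a reader would want them to have one meaning.

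**Working it through.** **1. Map the readings.** Each whole-unit reading was placed on both scales and tested against the Table 5 rule.

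| Largest reading (units) | Age 6 to <12 (SAP Table 3) | Age 12 to <65 (SAP Table 4) | Presence (SAP Table 5) |
|---|---|---|---|
| 1–4 | Grade 1 | no grade | Yes |
| 5–10 | Grade 2 | Grade 1 | Yes |
| 11–14 | Grade 2 | Grade 2 | Yes |
| 15–20 | Grade 3 | Grade 2 | Yes |
| 21+ | Grade 3 | Grade 3 | Yes |

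The gap is confined to 1–4 units from age 12.

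**2. Apply the presence rule.** A 3-unit reading is not none or absent, so the subject fails No. It is not a mixture of none and missing entries, so the subject fails Missing. What remains is Yes, and Yes subjects are in the denominator. The footnote to Table 5 derives presence and severe-or-greater reactions as separate variables, which fits a presence rule that does not pass through the grades.

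**3. What changes in the tables.** Let G subjects have a graded reaction and k subjects peak at 1–4 units, out of n. The count with the reaction is G + k and the grade rows sum to G, so the shortfall is k. Moderate and severe counts from age 12 do not depend on k, and pain is graded without calipers. For any local reaction, a subject adds to the shortfall only with no pain and no graded redness or swelling.

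**4. Size if a program required a grade.** The documents give no distribution of reaction sizes, so k and G are assumptions.

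(a) Ungraded subjects coded No and kept in the denominator: gap = (G + k)/n − G/n = k/n. For k = 1:
- adults: 1/150 = 0.67 points
- 6 to <18 group: 1/50 = 2.0 points
- 12 to <18 category: between 1/35 = 2.9 and 1/15 = 6.7 points, since the minimum of 15 per category in Protocol 3.3 leaves 15 to 50 − 15 = 35 subjects.

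With n = 150, G = 30 and k = 15: 45/150 = 30.0% (95% Clopper-Pearson 22.8–38.0) against 30/150 = 20.0% (13.9–27.3), a gap of 10.0 points.

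(b) Ungraded subjects in neither Yes nor No, and so dropped: gap = (G + k)/n − G/(n − k). With G = 30:
- k = 1: 31/150 − 30/149 = 20.67% − 20.13% = 0.53 points
- k = 15: 45/150 − 30/135 = 30.0% − 22.2% = 7.8 points.

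The simple k/n figure therefore holds only on route (a). On route (b) the gap is smaller and depends on G. On either route it is zero when k = 0.

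**The case for a change.** The strongest case for a change is that the protocol promises every reading will be classed as mild, moderate or severe, and the scale cannot do so for 1–4 units from age 12. The SAP does not define what it means to report a reaction relative to that scale. Two competent programmers could produce different primary proportions. Within the pooled 6 to <18 group the same reading is mild at one age and ungraded at another. A sentence and one extra table row would settle it.

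Much of this stands. The gap in the scale is real, and requiring Grade 1 for presence is a conceivable reading, though it is written nowhere.

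Three parts are weaker. First, SAP 6.1.1.1 does not list an any-severity row in the maximum-severity summary; there, any reaction means any type of reaction. The explicit any-day count is in the separate by-day summary. A single primary table that fails to add up is thus partly inferred. Second, the SAP states openly that the two paediatric scales differ and that each subject is graded on the scale for the age before pooling. That is a declared choice, not an oversight. Third, the natural remedy keeps the Table 5 and 6 rule. It would change no incidence and would only add a display row for subjects whom the plan already counts. The other remedy, Grade 1 or above as presence, would alter a primary endpoint definition and might need a protocol amendment under Protocol 9 and SAP 2, with no gain in the meaning of the result.

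**Conclusion.** No change is needed. The plan leaves unsaid how a sub-Grade-1 reaction from age 12 is displayed, but its presence rule, followed as written, yields a sound incidence with the right denominator and sound moderate and severe counts. An analyst who finds ungraded Yes subjects will see that the grade rows fall short by exactly their number and can show or footnote them in the output.

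The effect of the alternative coding is 0.67 points per subject in 150 adults if those subjects are coded No, and 0.53 points for one subject if that subject is dropped and 30 others are graded. The total cannot be found from the documents and may be zero. The analysis is descriptive (Protocol 9.1, SAP 5.1), so no decision rule depends on it. The conclusion rests on reading a recorded 1–4 unit measurement as a reported reaction, which is the plain sense of Tables 5 and 6.

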**Table 6. Derived Variables for Any Local Reaction Within the Time Interval**

Variable a	Yes (1)	No (0)	Missing (.)
Any day (Day 1 to Day 7 or 14)	Subject reports any reaction as yes (or present) on any day in the required interval.	Subject reports all reactions as none (or absent) for all days in the required interval.	Subject reports all reactions as a combination of none and missing for all days in the required interval.

- a. The variable will be derived for any local reaction (any of redness, swelling, and pain at the injection site) and for any severe or greater local reaction within Day 1 to Day 7 or 14 following vaccination.

**Other Reporting Summaries:**

➤ Subjects Reporting the Specific Reaction or Any Local Reaction on Each Day

The number of subjects reporting “yes” for at least 1 day or “no” for all days (these values are used as the denominators for the percentage calculations), number of subjects reporting at least 1 occurrence of the specified reaction or any reaction for that day (and any day), and observed proportion of subjects.

The above is repeated for moderate or severe reactions.

➤ Duration (Days) of Local Reactions

The number of subjects reporting “yes” for at least 1 day or “no” for all days, number of subjects reporting the specified reaction, mean, range (minimum, maximum), standard deviation, and number of unknown durations.

090177e190dce77Approved\Approved On: 06-May-2019 11:24 (GMT)

### **Analysis Specifications**

The number of subjects reporting the specified reaction, mean, range (minimum, maximum), and standard deviation will be calculated from the number of subjects reporting the specified reaction.

The duration of the specified reaction will be calculated as the number of days from the start of the first reported reaction to the resolution of the last reported reaction, inclusive. Resolution is the last day on which the reaction is recorded in the e-diary if the reaction lasted 7 days (6- to <18-year age group) or 14 days (18- to <65-year age group) or less, or the date on which the reaction ended if it continued beyond Day 7 or 14 (the latter will be collected on the CRF). If there is no known date when the reaction ended, then duration will be missing (unknown). Subjects with no reported reaction have no duration because it is not applicable.

➤ Duration (Total Days) of Local Reactions

The number of subjects reporting “yes” for at least 1 day or “no” for all days, number of subjects reporting the specified reaction, mean, range (minimum, maximum), standard deviation, and number of unknown durations.

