7.2.1. Local Reactions and Systemic Events

7.2.1.1. Electronic Diary

The subject will be issued an e-diary, based on a smartphone or equivalent technology. Starting on the day of vaccination, local reactions, systemic events, and any antipyretics or pain medication used to treat symptoms will be monitored by the subject's legally acceptable representative/parent/legal guardian for 7 days for subjects aged 6 to <18 years or by the subject for 14 days for subjects aged 18 to <65 years. The e-diary allows recording of these assessments only within a fixed time window, thus providing the accurate representation of the subject's experience at that time. Data on local reactions, systemic events, and antipyretics/pain medication used to treat symptoms reported in the e-diary will be transferred electronically to the e-diary vendor, where they will be available for review by investigators via an internet-based portal. At intervals agreed to by the vendor and Pfizer, the data will be transferred electronically into Pfizer's event database for analysis and reporting.

Investigators (or appropriately qualified designee) are required to review the e-diary data online at frequent intervals during e-diary periods, as part of the ongoing safety review.

The investigator or designee will obtain from the subject stop dates for any symptoms ongoing on the last day that the e-diary was completed. The stop dates will be documented in the source documents and the information entered in the CRF.

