### **Analysis Specifications**

The number of subjects reporting the specified reaction, mean, range (minimum, maximum), and standard deviation will be calculated from the number of subjects reporting the specified reaction.

The total days will be calculated as the sum total of reported days of the specified reaction. However, if the reaction continues beyond Day 7 or 14, the calculation of total days will include all days from the last e-diary day until the date of resolution collected on the CRF. If there is no known date when the reaction ended, then duration beyond Day 7 or 14 will be missing (unknown). Subjects with no reported reaction have no duration because it is not applicable.

➤ Summary of Day of Onset of Local Reactions

The number of subjects reporting the specified reaction or any reaction, mean, range (minimum, maximum), and standard deviation.

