**Reporting Summaries:**

For each systemic event, the below summary tables will be generated following the same rules as for local reactions in [Section 6.1.1.1](#), where applicable:

- Summary of Subjects Reporting Systemic Events by Maximum Severity Grade of the Events
- Subjects Reporting the Specific Event or Any Systemic Event on Each Day
- Duration (Days) of Systemic Events
- Duration (Total Days) of Systemic Events
- Summary of Day of Onset of Systemic Events

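### The SAP duration rule uses the CRF stop date only for reactions that run past Day 7 or 14, so a reaction that outlasts an early-stopped e-diary but ends inside the window is recorded as too short

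*SAP*

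**What the plan says.** SAP 6.1.1.1, under Duration (Days) of Local Reactions, gives two branches for the end of a reaction. In the first, "Resolution is the last day on which the reaction is recorded in the e-diary if the reaction lasted 7 days" (or 14 days in the older group) or less. The second is "or the date on which the reaction ended if it continued beyond Day 7 or 14 (the latter will be collected on the CRF"). It adds: "If there is no known date when the reaction ended, then duration will be missing (unknown").

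Under Duration (Total Days), the SAP sums the reported days of the reaction. It goes outside the diary on the same condition: "if the reaction continues beyond Day 7 or 14, the calculation of total days will include all days from the last e-diary day until" the CRF resolution date.

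SAP 6.1.1.2 lists "Duration (Days) of Systemic Events" and the matching total-days table, to be produced by the local-reaction rules where applicable. SAP 6.1.1.3 puts fever in the same tables.

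Protocol 7.2.1.1 sets the collection rule: "The investigator or designee will obtain from the subject stop dates for any symptoms ongoing on the last day that the e-diary was completed", with the date entered on the CRF. Protocol 6.1 asks the subject or guardian to note such dates, 6.3.1 repeats the reminder at unscheduled visits, and 6.2 has the site record the date, or confirm that the symptom is continuing, on the CRF at Visit 2. None of these sections makes collection depend on Day 7 or 14.

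**The concern.** The two documents use different triggers. The protocol asks whether the symptom was ongoing on the last day the diary was completed. The SAP asks whether the reaction went past the end of the scheduled diary window. The answers coincide for a subject who completes the diary to Day 7 or 14. They part when diary entry stops before then with the reaction present and the reaction ends inside the window. The CRF can then hold the end date, but the SAP takes the last diary day.

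The missed days cannot be filled in later, because Protocol 7.2.1.1 says the diary accepts entries only within a fixed time window. The resulting error can only shorten a duration. Where a stop date was obtained, the subject also has a numerical duration and so would not appear in the table's count of unknown durations. At stake are individual duration values and the reported range, which would then depend partly on diary compliance.

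**Working it through.** **Inputs from the documents.** Day 1 is the day of vaccination. The window W is 7 days (6 to <18 years) or 14 days (18 to <65 years). Duration is counted inclusively from the first reported day to resolution. The plan states no duration figure, so there is nothing of its own to reproduce.

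**The rule as written.** Let o be the onset day, l the last diary day with the reaction (here also the last completed diary day), and s the CRF stop day.

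- SAP: duration = s − o + 1 if s > W; otherwise l − o + 1.
- Using the stop date the protocol collects: duration = s − o + 1.
- Understatement when s ≤ W: s − l.

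**Worked cases, onset Day 1**

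| Group | Last diary day | CRF stop day | SAP | With CRF date |
|---|---|---|---|---|
| 6 to <18 | 3 | 6 | 3 | 6 |
| 6 to <18 | 3 | 8 | 8 | 8 |
| 18 to <65 | 5 | 10 | 5 | 10 |
| 18 to <65 | 3 | 12 | 3 | 12 |
| 18 to <65 | 3 | 14 | 3 | 14 |
| 18 to <65 | 3 | 15 | 15 | 15 |

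For an adult whose last entry is Day 3, every stop date from Day 4 to Day 14 gives 3 days, and Day 15 gives 15. That is a jump of 12 days for one extra day of reaction. Total days behaves the same way in these cases.

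**Largest understatement.** With o = l = 1 and s = W, it is 7 − 1 = 6 days, or 14 − 1 = 13 days.

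**Effect on a mean.** The shift is f × d, where f is the share of reactors affected and d the mean days lost by each. The documents give neither, so both are assumed.

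- Simulation with geometric durations (p = 0.3, mean 3.3 days), onset Day 1 or 2, and 5% to 20% of adults stopping the diary at a uniformly distributed day from 1 to 13: f is 0.9% to 3.4%. Mean duration among those affected falls from about 6.1 to 3.0 days, so d is about 3.1. The shift is 0.009 × 3.1 = 0.03 to 0.034 × 3.1 = 0.10 day.
- The same assumptions with a 7-day window: f is 1.2% to 4.9%, and the affected durations are roughly halved from about 4.3 days.
- A deliberately wide range, f = 2% to 20% and d = 1 to 5 days: 0.02 × 1 = 0.02 to 0.20 × 5 = 1.0 day. The upper end needs one reactor in five to be affected, well beyond the simulated scenario.

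If all 150 adults reacted, 150 × 0.009 to 150 × 0.034 is about 1 to 5 people.

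**Small categories.** SAP 6.1.1.1 also compiles these summaries by age category, with minimum enrolments of 15 and 50. One worst-case subject would move the mean by 6/15 = 0.4 day among 15 child or adolescent reactors, or 13/50 = 0.26 day among 50 adult reactors.

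**A second ambiguity in the same sentence.** The first branch is worded by length and the second by calendar day. A child's reaction from Day 3 to Day 8 lasts 8 − 3 + 1 = 6 days and runs past Day 7, so it meets both.

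**The case against.** The best defence is that Protocol 6.1 instructs diary completion through Day 7 or Day 14, so the last completed day can be read as the scheduled last day. The documents then agree, and early stopping is simply a case neither addresses. That works only for fully compliant subjects. The SAP itself expects incomplete diaries: Tables 5 and 6 define a category of none combined with missing, and 6.5.7 tabulates completion day by day. The same table would make poor compliance visible, though not its effect on duration.

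Four further points stand, wholly or in part.

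- **Total days.** This is by definition a sum of reported days, so leaving out unreported days inside the window is not plainly an error. It shares the trigger but needs its own wording.
- **No stop date obtained.** The SAP's unknown-date sentence might make the duration missing. The text does not say whether it overrides the last-diary-day branch.
- **Data quality.** The diary is contemporaneous. The CRF date is subject-reported and may be obtained as late as Visit 2 (Day 29 to 43), although subjects are asked to note it. Preferring diary data is defensible, but the SAP already accepts the CRF date for longer reactions.
- **Fever.** Protocol 7.2.1.5 has temperature collected daily until fever resolves, so the gap may arise less often there.

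A reader might infer that the primary safety results are biased in a reassuring direction. The documents do not support this. Duration sits under Other Reporting Summaries, whereas the primary endpoints are incidence and severity, which use different derivations. No hypothesis or decision rule depends on duration.

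**Conclusion.** The point holds as a minor defect in a derivation rule. Read literally, SAP 6.1.1.1 gives too short a duration when three things coincide: diary entry stopped before Day 7 or 14, the reaction was present at the last completed entry, and it ended within the window. The per-subject bounds of 6 and 13 days follow from the text alone. The overall shift of about 0.03 to 0.10 day rests on assumed early-stop rates and an assumed duration distribution. The practical effect is therefore on individual values and the reported maximum, mainly in the small age categories, and hardly on the headline mean.

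It would be too strong to say that the SAP ignores the CRF stop date in general, since it uses it for every reaction continuing past the window. It would also be too strong to say that the protocol expressly provides for early diary stopping: its wording covers that case but does not discuss it.

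**What to change.** In SAP 6.1.1.1, replace the Day 7/14 condition for Duration (Days) with wording such as:

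> *If the reaction was present on the last day the e-diary was completed, resolution is the stop date collected on the CRF, and duration is unknown if no stop date was obtained; otherwise resolution is the last e-diary day on which the reaction was recorded.*

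Word Duration (Total Days) separately:

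> *If the reaction was present on the last day the e-diary was completed, total days is the sum of reported days plus the days after that last e-diary day through the CRF stop date; if no stop date was obtained, the days beyond the last e-diary day are unknown.*

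Apply the same trigger to systemic events, including fever, where a CRF stop date exists. This also removes the overlap between length and calendar day.

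The cost is SAP wording and a small programming change; the protocol already collects the dates. The drawback is heavier reliance on a subject-reported date that may be obtained only at Visit 2.
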